# **Tolerance to residual astigmatism and defocus in eyes with a non-diffractive extended depth of focus (EDoF) intraocular lens**

## **INTRODUCTION**

Multifocal intraocular lenses have been shown to be a good option for cataract surgeons aiming to offer improved vision at different distances. Trifocal IOLs provide enhanced vision at far, intermediate and near distances and have overcome the characteristic V-pattern with 2 peaks corresponding to near and far vision provided by bifocal IOLs. Although multifocal IOLs could increase spectacle independence in patients undergoing cataract surgery, these lenses could also increase some visual disturbances such as glare or haloes.

“Extended depth of focus” (EDoF) IOLs are currently available for cataract surgeons. They employ different optical technologies to achieve extended vision, increasing the range of vision while minimizing visual disturbances induced by classical diffractive multifocal designs. In fact, current clinical results show that EDoF lenses could increase the range of vision from far to intermediate distances and reduce the perception of visual disturbances of the patients.

In addition, while it has been reported that issues such as biomechanical properties of the cornea, inaccurate calculations, or misalignments of the IOLs may lead into residual refractive errors that will likely decrease the visual quality of patients with bifocal or trifocal IOLs, less is known about their impact on EDoF designs.

Therefore, regardless of the optical improvements achieved by EDoF lenses, better knowledge of the spherical and/or astigmatic tolerance of EDoF IOLs is crucial

for an appropriate surgical planning and for avoiding postoperative refractive corrections. Thus, the aim of this study is to analyze the impact of mild amounts of residual spherical defocus and astigmatism in patients implanted with a novel non-diffractive EDoF IOL.

## **PATIENTS AND METHODS**

Prospective study, which will include patients undergoing bilateral cataract surgery with bilateral implantation of a Vivity non-toric lens

Performed at Clínica Rementería, Madrid, Spain

Inclusion criteria:

-Patients >40 years old undergoing bilateral cataract surgery with Vivity IOL implantation

Exclusion criteria:

- corneal astigmatism  $\geq 1.0$  diopters (D)
- amblyopia
- previous ocular surgery
- presence of ocular pathologies
- abnormal iris
- intra- or postoperative complications
- postoperative distance corrected visual acuity (DCVA)  $< 20/20$
- postoperative refractive astigmatism  $> 0.50D$ .

### **Postoperative clinical assessment**

Patients will be evaluated one day, one week, one month, and three months postoperatively. Patients fulfilling inclusion criteria will be approached to be included in the study at the three-month visit.

Explorations to be performed at the three-month visit

- Uncorrected distance, intermediate (60cm) and near (40cm) visual acuity (VA) with an ETDRS chart, followed by subjective refraction.
- Once the best distance correction is obtained, further VA evaluation procedures will be performed with the FrACT3.9.9a version of the Freiburg Acuity Test software package. Once patients achieve the best distance correction (reference situation), a monocular analysis of VA at distance vision will be conducted under different induced conditions.
  - both a myopic and hyperopic defocus of 0.50 D will be simulated
  - after these measurements, a mixed astigmatism with different orientation will also be induced by adding a combination of -0.25 diopter (D) spherical and 0.50 D cylindrical lenses placed in vertical (against the rule - ATR), oblique and horizontal (with the rule – WTR) positions.

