### **Statistical Analysis**

The calculation of the required sample size was based on monocular CDVA. A difference of 0.2 logMAR units was assumed to be clinically significant and a standard deviation of 0.05 was considered. Based on this assumption and  $\alpha$  of 0.05 and power of 0.8, it was calculated that 25 eyes were required.

Data analysis will be performed using SPSS for Windows V.20.0 (SPSS Inc, Chicago, IL). The normal distribution of variables will be assessed using the Kolmogorov-Smirnov test. A repeated-measures analysis of variance (ANOVA) will be

used to gauge any statistically significant difference within the different situations. Post hoc multiple comparison testing will be performed using the Holm-Sidak method. Differences will be considered to be statistically significant when the P value is  $<0.05$  (i.e., at the 5% level).

Protocol approved by Hospital Clínico San Carlos, code C.I. 21/365-O\_P

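### Acuity conditions are tested in the same block order in every eye with no order control, so practice or fatigue could bias comparisons between reference, defocus and astigmatism

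*Combined protocol and SAP*

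**What the plan says.** The section on postoperative clinical assessment puts ETDRS acuity and subjective refraction first, then the FrACT tests: "Once patients achieve the best distance correction (reference situation), a monocular analysis of VA at distance vision will be conducted under different induced conditions". The first induced pair is spherical: "both a myopic and hyperopic defocus of 0.50 D will be simulated". The astigmatic conditions follow: "after these measurements, a mixed astigmatism with different orientation will also be induced", using "cylindrical lenses placed in vertical (against the rule - ATR), oblique and horizontal (with the rule – WTR) positions". That makes six conditions per eye: one reference, two defocus and three astigmatic.

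Defocus before astigmatism is explicit. The reference reading coming first is implied by the wording but not stated. The order of the two defocus signs, and of the three orientations, is not given.

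The Statistical Analysis section plans a repeated-measures ANOVA, "used to gauge any statistically significant difference within the different situations", and adds: "Post hoc multiple comparison testing will be performed using the Holm-Sidak method". It names no period or order term. Neither section mentions randomised order, counterbalancing, a practice run or a repeat of the reference reading.

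**The concern.** In a within-eye comparison the order of testing is a design factor. If acuity drifts over a run of tests, through learning the task or through tiring, a condition that is always tested late carries that drift into its mean. Here the block sequence is identical in every eye, so the drift does not average out and more eyes will not remove it.

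The affected contrasts are those that serve the study's aim: reference against defocus, reference against astigmatism, and defocus against astigmatism. The direction cannot be predicted. Practice would make the late-tested astigmatic conditions look better tolerated than they are; fatigue would make them look worse. Contrasts inside a block (myopic against hyperopic, or one orientation against another) are not at issue, because the plan does not fix their order.

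**Working it through.** The plan gives no figure for practice or fatigue, so there is none to reproduce. The drift sizes below are assumptions. The 25 eyes are taken as planned and treated as independent.

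**1. Is condition separable from position?** With the reference first, the positions are 1 (reference), 2–3 (defocus) and 4–6 (astigmatism). The mean positions are 1, (2+3)/2 = 2.5 and (4+5+6)/3 = 5, whatever the order inside a block. The gaps are:

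- reference to defocus: 1.5
- defocus to astigmatism: 2.5
- reference to astigmatism: 4

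Consider a model with eye, condition and free position effects. Even if order inside each block were fully balanced, its design matrix is 2 short of full rank. The two missing dimensions are the two block contrasts.

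**2. Could a linear drift term rescue the analysis?** Only at a price. With balanced order inside the blocks, the within-eye position sum of squares available to estimate the slope is 0.5 (defocus) + 2 (astigmatism) = 2.5. The variance of a contrast is multiplied by 1 + (gap²/2.5)/v, where v is the contrast's own variance factor:

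| Contrast of block means | v | Multiplier |
|---|---|---|
| Reference – defocus | 1 + 1/2 = 1.5 | 1 + (1.5²/2.5)/1.5 = 1.6 |
| Defocus – astigmatism | 1/2 + 1/3 = 0.833 | 1 + (2.5²/2.5)/0.833 = 4.0 |
| Reference – astigmatism | 1 + 1/3 = 1.333 | 1 + (4²/2.5)/1.333 = 5.8 |

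**3. What would a drift do to the tests?** The plan says: "A difference of 0.2 logMAR units was assumed to be clinically significant and a standard deviation of 0.05 was considered". It does not say whether 0.05 is the SD of a paired difference or of a single reading, so both are shown. If it applies to single, uncorrelated readings, the SD of the difference is 0.05 × √2 = 0.0707. With n = 25 the standard error is 0.05/5 = 0.0100 or 0.0707/5 = 0.0141.

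The number of post hoc pairs is also not stated: 5 against reference, or all 15. The first Holm-Sidak thresholds are 1 − 0.95^(1/5) = 0.01021 and 1 − 0.95^(1/15) = 0.00341.

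The table gives the two-sided rejection probability (noncentral t, 24 df, noncentrality = shift/SE) with no true effect and a drift-induced shift between the two conditions compared:

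| SD of difference | Threshold | No shift | 0.01 | 0.02 | 0.03 logMAR |
|---|---|---|---|---|---|
| 0.05 | 0.05 | 5% | 16% | 48% | 82% |
| 0.05 | 0.01021 | 1% | 5% | 24% | 59% |
| 0.05 | 0.00341 | 0.3% | 2% | 14% | 42% |
| 0.0707 | 0.05 | 5% | 10% | 27% | 53% |
| 0.0707 | 0.01021 | 1% | 3% | 11% | 28% |
| 0.0707 | 0.00341 | 0.3% | 1% | 5% | 16% |

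These shifts are 5%, 10% and 15% of the plan's 0.2 logMAR.

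**4. What would counterbalancing achieve?** A 6×6 Williams square is exactly balanced at 24 or 30 eyes. At 25 eyes one row is used once more than the others, and mean positions differ by at most 0.2 of a place. That is 0.2/5 = 4% of a linear first-to-last drift: 0.04 × 0.03 = 0.0012 logMAR for a drift of 0.03. The model in step 1 then has full rank at 24, 25 and 30 eyes, and the variance multiplier in step 2 is 1.00.

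**The case against.** The strongest reply is that no drift has been shown, and that the table applies one shift to contrasts with unequal gaps. If drift is linear and totals 0.03 logMAR from first test to last, the shifts are 0.03 × 1.5/5 = 0.009 (reference–defocus), 0.03 × 2.5/5 = 0.015 (defocus–astigmatism) and 0.03 × 4/5 = 0.024 (reference–astigmatism). With an SD of 0.05, rejection is then 14/30/63% unadjusted and 2/6/23% at the first step of 15. With 0.0707 it is 9/17/37% and 1/2/8%. Reference against defocus is barely exposed on that scale. This stands as a guide to reading the table: its columns are shifts between two conditions, not drifts across the session. It does not clear the plan. In a simulation of that same linear drift, with the ANOVA used as a gate and Holm-Sidak over all 15 pairs, at least one false difference was declared in about 52% of studies (SD 0.05) or about a quarter (0.0707). With a first-to-last drift of 0.01 the figures were 6% and 4%.

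Three further points have some weight. ETDRS testing and refraction come before the FrACT series and may blunt early practice effects, but they are not FrACT familiarisation and could add fatigue. The 0.2 logMAR criterion is not threatened by drifts of this size; that is true, but the plan declares differences by P < 0.05, and the study concerns mild refractive errors. Finally, if the reference FrACT reading were used to confirm the postoperative acuity criterion, moving it would delay that check. The documents do not say that it is used in this way.

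**Conclusion.** The concern holds. The plan prescribes a block sequence that is the same in every eye and has no order control in design or analysis, so every contrast between blocks is confounded with test position. That conclusion rests on the text; for contrasts involving the reference it also relies on the implied reading that the reference is tested first.

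The size of any bias is unknown. The rejection rates depend on assumed shifts of 0.01–0.03 logMAR, on how the SD of 0.05 is read, on the number of post hoc pairs, and on 25 independent eyes. Within those ranges the effect runs from slight to severe. It bears on statistical significance and on small differences between conditions, including small true losses that practice could hide. It would not create or remove a 0.2 logMAR loss. The change should be made before data collection, because the analysis can recover the block contrasts only by assuming a form for the drift and accepting a loss of precision.

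**What to change.** After subjective refraction, replace the block sequence with a randomised or counterbalanced order, per eye, of all six conditions, including the FrACT reading at best correction. A 6×6 Williams square is one way to do this and works at the planned 25 eyes. State the scheme in the section on postoperative clinical assessment and record the order used for each eye. Optionally, add test position as a factor, with a mixed model in place of the repeated-measures ANOVA.

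The cost is a pre-printed order list per eye. No extra patients are needed, and no extra readings if the reference FrACT reading is already taken, as the plan implies. The downsides are a varying lens order for the examiner and, if the position term is used, slightly more analysis work. If the acuity criterion is to be confirmed by the FrACT reference reading, the protocol should say so, so that the order scheme can allow for it.

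A lighter alternative is to keep the sequence and repeat the reference reading at the end, at one extra reading per eye. That would allow a check for drift but would not remove the confounding.

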### **Statistical Analysis**

The calculation of the required sample size was based on monocular CDVA. A difference of 0.2 logMAR units was assumed to be clinically significant and a standard deviation of 0.05 was considered. Based on this assumption and  $\alpha$  of 0.05 and power of 0.8, it was calculated that 25 eyes were required.

Data analysis will be performed using SPSS for Windows V.20.0 (SPSS Inc, Chicago, IL). The normal distribution of variables will be assessed using the Kolmogorov-Smirnov test. A repeated-measures analysis of variance (ANOVA) will be

used to gauge any statistically significant difference within the different situations. Post hoc multiple comparison testing will be performed using the Holm-Sidak method. Differences will be considered to be statistically significant when the P value is  $<0.05$  (i.e., at the 5% level).

Protocol approved by Hospital Clínico San Carlos, code C.I. 21/365-O\_P

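### The 25 eyes do not follow from the stated difference, SD, alpha and power; the figures must be reconciled before the plan says what 25 eyes can detect

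*Combined protocol and SAP*

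**What the plan says.** All references are to the combined protocol and SAP.

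- **Sizing endpoint** (Statistical Analysis): "The calculation of the required sample size was based on monocular CDVA".
- **Inputs** (same section): "A difference of 0.2 logMAR units was assumed to be clinically significant and a standard deviation of 0.05 was considered". The SD carries a citation to reference 12. The reference list as printed ends at 11.
- **Result** (same section): alpha is 0.05 and, with "power of 0.8, it was calculated that 25 eyes were required". The section names no test or formula for this calculation. It does not give sidedness or SD type, and it states no allowance for loss, multiplicity or fellow eyes.
- **Design** (Postoperative clinical assessment): after best distance correction, "a monocular analysis of VA at distance vision will be conducted under different induced conditions". The conditions are two of defocus and three of astigmatism. With the reference that makes six conditions in each eye.
- **Analysis** (Statistical Analysis): "A repeated-measures analysis of variance (ANOVA) will be" the main test, and "Post hoc multiple comparison testing will be performed using the Holm-Sidak method". The set of comparisons is not named.

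**The concern.** The sample size is presented as the output of four stated inputs. A difference of 0.2 with an SD of 0.05 is four standard deviations (0.2 / 0.05 = 4). In a within-eye comparison an effect that large needs only a handful of eyes, so 25 looks out of line.

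The size justification is the plan's only statement of what the study can detect. If its figures disagree, a reader cannot tell whether 25 eyes were chosen for 0.2 logMAR, for some smaller difference, or with a different SD. Those possibilities lead to very different power.

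**Working it through.** **Inputs from the document.** Difference d = 0.2 logMAR; SD = 0.05; alpha = 0.05; power = 0.8; stated N = 25 eyes; six conditions per eye.

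**Assumptions, because the plan is silent.** Tests are two-sided and eyes independent, with equal SD across conditions. The SD of the within-eye difference, s, is taken two ways:
- s = 0.05, if 0.05 is already the SD of the difference;
- s = 0.05 × √2 = 0.0707, if 0.05 is the per-condition SD and the correlation is zero.

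**Step 1: try to reproduce 25 with a paired t-test.** Power comes from the noncentral t distribution with n − 1 degrees of freedom and noncentrality (d / s) × √n.
- s = 0.05, n = 3: noncentrality 4 × √3 = 6.93, power 0.908. With n = 2, power is 0.343. **3 eyes are needed.**
- s = 0.0707, n = 4: noncentrality 2.83 × √4 = 5.66, power 0.950. With n = 3, power is 0.705. **4 eyes are needed.**

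**Step 2: allow for Holm-Sidak.** The first-step level is 1 − 0.95^(1/m). Five comparisons with the reference give 0.0102. All 15 pairs of six conditions give 0.0034.

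| First step | Eyes, s = 0.05 (power) | Eyes, s = 0.0707 (power) |
|---|---|---|
| m = 5 | 4 (0.856) | 5 (0.860) |
| m = 15 | 5 (0.901) | 6 (0.849) |

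**Step 3: size on the repeated-measures ANOVA.** The harshest variant tried has six conditions, zero correlation, lower-bound sphericity correction (epsilon = 1/5 = 0.2), and a 0.2 range with the other four means at the midpoint.
- Sum of squared deviations: 0.1² + 0.1² = 0.02.
- Noncentrality: n × (0.02 / 0.05²) × 0.2 = 1.6n, on 1 and n − 1 degrees of freedom.
- n = 7: noncentrality 11.2, power 0.795. n = 8: noncentrality 12.8, power 0.864. **8 eyes are needed.**

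**Step 4: look for another route to 25.**
- Loss to follow-up: from 8 eyes it would take 1 − 8/25 = 68%; from 3 eyes, 1 − 3/25 = 88%.
- Fellow eyes: doubling 8 for fully correlated pairs gives 16.
- Independent groups: a two-sample t-test needs 3 per arm (5 per arm at alpha/15). A six-group one-way ANOVA needs 3 per group, 18 in all.

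None of these gives 25.

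**Step 5: what 25 eyes deliver if 0.05 is right.** Power for 0.2 is essentially 1.00. The change detectable with 80% power, in logMAR, is:

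| Comparison set | s = 0.05 | s = 0.0707 |
|---|---|---|
| Unadjusted | 0.029 | 0.041 |
| First Holm-Sidak step of 5 | 0.037 | 0.052 |
| First Holm-Sidak step of 15 | 0.041 | 0.059 |

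The range 0.029 to 0.059 is 15% to 29% of 0.2.

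**Step 6: what follows if another figure is wrong.** These are illustrations, not facts about the trial; tests are unadjusted.
- SD wrong, 0.2 right: 25 eyes give 80% power for 0.2 when s is about 0.34, which is 6.85 times 0.05.
- Difference wrong, for example 0.02 with SD 0.05: 25 eyes have power 0.48 (s = 0.05) or 0.27 (s = 0.0707). With s = 0.05, 52 eyes would be needed.
- A difference near 0.03 with s = 0.05 gives 24 eyes, close to 25, but the document nowhere states 0.03.

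**The case against.** The strongest reply is that 25 eyes are ample on the printed figures, so nothing planned at 0.2 logMAR is at risk and this is only a documentation slip. That holds if the SD of 0.05 is right. But the document gives no means of confirming it, since the cited source is absent from the printed list, and step 6 shows that the answer changes when a different figure is the wrong one.

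For the same reason, a reader might infer that the study is oversized, that 0.2 misstates its sensitivity, or that 25 should simply be kept. The documents do not support any of these outright. With an SD of the within-eye difference near 0.34, 0.2 is about what 25 eyes detect. With an intended difference of 0.02, 25 eyes would be too few.

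A reader might also infer that the plan treats any significant P value as clinically important. It does not. It sets the two notions apart: "A difference of 0.2 logMAR units was assumed to be clinically significant" is one statement, and "Differences will be considered to be statistically significant when the P value is" below 0.05 is another. Reading significant changes against 0.2 is sound reporting advice, not a correction of something the plan claims.

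Finally, 8 eyes is the harshest variant tried, not a proven ceiling. It assumes independent eyes, while the plan enrols bilaterally implanted patients and does not limit the study to one eye each. Correlated fellow eyes could raise the need and enlarge the detectable changes in step 5. Even the doubled figure of 16 falls short of 25, so the mismatch remains.

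**Conclusion.** The stated sample size does not follow from its stated inputs. They need 3 or 4 eyes in a paired comparison, 4 to 6 at the first Holm-Sidak step, and 8 in the harshest ANOVA variant tried, against 25 in the plan. This rests on two-sided tests, equal SDs and independent eyes. The unstated choices of SD type and comparison set were varied, and none brought the answer near 25.

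Which figure is in error cannot be settled from the documents. The direction of the error and the detectable changes in step 5 are therefore conditional on 0.05 being confirmed. The point should be fixed, because the sizing sentence is wrong as written and the true power of 25 eyes depends on the answer.

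**What to change.** 1. Reconcile the difference, the SD and the N. State the test and sidedness, whether 0.05 is the SD of the within-eye difference or of a single condition, its source (adding reference 12 to the list), the comparison set, and whether one or both eyes of a patient may enter.
2. If 0.05 is confirmed and eyes are independent, replace the sizing sentence with, for example: *With 25 independent eyes and two-sided alpha 0.05, the study has 80% power to detect a mean within-eye change of [value] logMAR, taking 0.05 as [SD type] and testing [comparison set]. A change of 0.2 logMAR is the clinical threshold, and statistically significant changes will also be read against it.* Take the value from the table in step 5.
3. If the SD or the difference proves to be the misprinted figure, recompute and state the power that 25 eyes actually give.

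The cost is one rewritten paragraph. Whether 25 eyes remain enough can be judged only after step 1.

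### Does leaving the Holm-Sidak family of comparisons unnamed weaken the analysis?

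*Combined protocol and SAP*

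**What the plan says.** The Introduction states that "the aim of this study is to analyze the impact of mild amounts of residual spherical defocus and astigmatism". The section on postoperative assessment sets up six viewing conditions per eye. One is best distance correction, which it calls the reference ("Once patients achieve the best distance correction (reference situation"). Two are spherical defocus of 0.50 D, myopic and hyperopic. Three are induced mixed astigmatism: against the rule, oblique and with the rule.

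The Statistical Analysis section plans a repeated-measures ANOVA, "used to gauge any statistically significant difference within the different situations", and then: "Post hoc multiple comparison testing will be performed using the Holm-Sidak method". It gives no list or number of comparisons and no error term for the post hoc tests. On size it says "A difference of 0.2 logMAR units was assumed to be clinically significant and a standard deviation of 0.05 was considered", and with alpha 0.05 and "power of 0.8, it was calculated that 25 eyes were required".

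**The concern.** Holm-Sidak compares the smallest p-value with a threshold that depends on how many tests are in the family, so naming the method without the family leaves the procedure incomplete. Two readings are open. The named reference and the word impact in the aim suggest five contrasts, each induced condition against best correction. An ANOVA for any difference followed by post hoc testing suggests all 15 pairs.

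Two things could be at stake. First, if only the five contrasts matter, testing all 15 pairs gives away power. In a tolerance study a contrast that misses significance may be read as evidence that the error is tolerated. Second, an unnamed family could in principle be chosen after the results are known, and that would inflate the familywise error.

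**Working it through.** **Inputs from the plan.** Six conditions; 25 eyes; family-level alpha 0.05 (two-sided assumed); difference 0.2 logMAR; SD 0.05. The plan does not say whether 0.05 is the SD of a single acuity or of a paired difference. If it is per condition with correlation r, the SD of the difference is 0.05 × √(2(1 − r)): 0.050 at r = 0.5 and 0.071 at r = 0.

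**Assumptions made here.** 25 independent eyes, paired t-tests unless stated otherwise, and small losses of 0.03 and 0.05 logMAR for illustration.

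**The plan's own figure.** A paired t-test for 0.2 logMAR at 80% power needs 3 eyes with an SD of differences of 0.05, or 4 with 0.071. The stated 25 does not follow from the stated inputs. That is a separate matter. Here it means only that the study has far more eyes than its own target difference requires.

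**Size of each family.** All pairs: 6 × 5 / 2 = 15. Against the reference: 5. The five plus myopic against hyperopic and the three between-orientation pairs: 9.

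**First-step thresholds and power.** The threshold is 1 − 0.95^(1/m), and the critical t has 24 df. The noncentrality is loss / (SD / √25). With SD 0.05 this is 0.03 / 0.01 = 3 for a loss of 0.03, and 0.2 / 0.01 = 20 for the plan's 0.2. With SD 0.071 and a loss of 0.2 it is 14.1.

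| Family | First-step alpha | Critical t | Power at 0.03, SD 0.05 | Power at 0.2, either SD |
|---|---|---|---|---|
| 5 | 0.0102 | 2.79 | 0.589 | 1.00 |
| 9 | 0.0057 | 3.04 | 0.499 | 1.00 |
| 15 | 0.0034 | 3.25 | 0.423 | 1.00 |

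The loss detectable with 80% first-step power at SD 0.05 is 0.037 logMAR with five contrasts and 0.041 with 15 pairs, a difference of 0.004.

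**Full step-down, simulated, one condition worse.**
- Loss 0.03, SD of differences 0.05: 0.59 (five), 0.51 (nine), 0.44 (15).
- The same with the ANOVA's pooled error: about 0.65 (five) against 0.53 (15).
- Loss 0.05, SD 0.05: 0.98 (five) against 0.96 (15).
- Loss 0.05, SD 0.071: 0.76 (five) against 0.64 (15).
- Loss 0.2: 1.00 under either family.

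The gap depends on the pattern of losses. With all five conditions worse by 0.03 at SD 0.05 it is 0.70 against 0.44.

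**Familywise error with no true differences.** 15 pairs 4.2%; nine 4.5%; five 4.4%. Five contrasts plus a separate family of four: 8.3% over both. Choosing between five and 15 after seeing the results: 6.7%; choosing among five, nine and 15: 7.3%.

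**The case for a change.** The best case for acting is that the direction needs no assumed effect. The five contrasts are a subset of the 15 pairs, so with the same p-values any contrast rejected in the larger family is also rejected in the smaller one. The study concerns mild refractive errors in eyes selected for good corrected acuity, so losses well below 0.2 logMAR are plausible, and at those losses the gap can be sizeable. Naming the family would take a sentence or two and no new data. It would also close off a choice made after the fact, which is a genuine error-rate matter: 6.7% instead of 5%.

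All of that stands as a matter of good practice. It does not make the plan unsound. The plan gives no sign of switching families, and the inflation arises only if someone does so. The power gap concerns a loss less than one sixth of the difference the plan treats as important (0.03 / 0.2 = 0.15), and its size depends on the SD, the error term and the pattern of losses, none of which the plan settles.

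Nor is the narrower family plainly better. Astigmatism is induced in three separate orientations, so comparisons between orientations plausibly belong to the aim. Putting them in a second family raises overall error to about 8.3% and leaves six pairs descriptive. Keeping them in one family of nine brings the gain down to 0.51 against 0.44.

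**Conclusion.** No change follows. The family is not named, but an analyst would fill that gap in the ordinary way, with all 15 pairs after an ANOVA across six conditions. That reading controls familywise error (about 4.2%) and has power of essentially 100% at 0.2 logMAR with an SD of differences of either 0.05 or 0.071. A five-contrast family is a legitimate efficiency choice for small losses: 0.59 against 0.44 at 0.03 logMAR, or about 0.65 against 0.53 with pooled error. It is paid for in formal tests between induced conditions or in overall error control.

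These small-loss figures rest on 25 independent eyes, an SD of differences of 0.05, one affected condition and a loss the plan does not name. The conclusion also assumes that one family is used throughout and is not picked from the results.

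### The study asks how much acuity is lost to residual error, but the only planned inference is P < 0.05; mean change from reference with a simultaneous confidence interval should be the main result

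*Combined protocol and SAP*

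**What the plan says.** The title is "Tolerance to residual astigmatism and defocus in eyes with a non-diffractive extended depth of focus (EDoF) intraocular lens". The Introduction says that "better knowledge of the spherical and/or astigmatic tolerance of EDoF IOLs is crucial" "for an appropriate surgical planning and for avoiding postoperative refractive corrections", and that "the aim of this study is to analyze the impact of mild amounts of residual spherical defocus and astigmatism".

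Under Postoperative clinical assessment, best distance correction is the reference situation, and "a monocular analysis of VA at distance vision will be conducted under different induced conditions". Five conditions are induced: myopic and hyperopic defocus of 0.50 D, and mixed astigmatism in three orientations.

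The Statistical Analysis section plans a normality check, a repeated-measures ANOVA for any difference among the situations, and Holm-Sidak post hoc comparisons. The rule for reading them is "Differences will be considered to be statistically significant when the P value is" below 0.05. The comparisons are not listed, and the reference situation is not named as comparator. The one statement of what matters clinically is in the sample-size paragraph: "A difference of 0.2 logMAR units was assumed to be clinically significant". It is not used again.

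**The concern.** Tolerance and impact are matters of how much. A surgeon planning a target refraction needs the number of logMAR lost with 0.50 D of residual error and the precision of that number. A P value answers whether there is any loss. The design supplies what the size question needs, a reference and five induced conditions in the same eye, but the analysis section does not turn it into an estimate with an interval.

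What is at stake is how the result will be read. A significant comparison may reflect a loss far below the plan's own threshold. A non-significant one may still leave a smaller loss open. The planned inference does not tell these situations apart.

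**Working it through.** **1. Question against analysis.** Title and Introduction: tolerance, impact, use in surgical planning. Statistical Analysis: global test, adjusted pairwise tests, P < 0.05. No effect estimate, interval or tolerance criterion is planned. This part needs no arithmetic.

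**2. Number of comparisons.** One reference, two defocus and three astigmatism conditions make 6 levels. That gives 5 contrasts with reference, or 6 × 5 / 2 = 15 pairs. The plan does not say which family is used; 15 is the case of all pairs.

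**3. The plan's own figure.** Inputs: 0.2 logMAR, SD 0.05, alpha 0.05, power 0.8; stated result 25 eyes. It does not reproduce. An exact two-sided paired t calculation gives 3, 4 and 5 eyes for a difference SD of 0.05, 0.071 and 0.10. That is a separate matter, and 25 eyes are taken as given below.

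**4. SD of the within-eye difference.** The plan does not say what its 0.05 describes. Three values are used:
- 0.05, if it is already the SD of a difference;
- 0.05 × √2 = 0.071, if it is the SD of one reading, with equal variances and zero correlation;
- 0.10, our assumption.

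Eyes are treated as independent, each contrast uses its own SD (df 24), and tests are two-sided.

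**5. Smallest observed loss that is significant** = t × SD / √25.
- Unadjusted: t = 2.064.
- First Holm-Sidak step over 15 pairs: alpha = 1 − 0.95^(1/15) = 0.0034, t = 3.249.

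| | SD 0.05 | SD 0.071 | SD 0.10 |
|---|---|---|---|
| Unadjusted | 0.021 | 0.029 | 0.041 |
| First step of 15 | 0.032 | 0.046 | 0.065 |

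Against 0.2 logMAR these run from 0.021/0.2, about 10%, to 0.065/0.2, about a third.

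**6. What a non-significant comparison leaves open.** For five simultaneous intervals, alpha = 1 − 0.95^(1/5) = 0.0102 and t = 2.788. The largest observed loss that just fails the first step of 15 is 3.249 × SD/5. Adding the half-width 2.788 × SD/5 gives an upper limit of 6.037 × SD/5 = 0.060/0.085/0.121. So 0.2 is excluded at these three SDs. It would not be excluded once the SD exceeds 0.2 × 5 / 6.037 = 0.166.

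**7. Is the interval precise enough?** Half-width = 2.788 × SD/5 = 0.028/0.039/0.056 with independent eyes. Patients have "patients undergoing bilateral cataract surgery with bilateral implantation of a Vivity non-toric lens", so both eyes may count, although the plan does not say. Suppose 12 patients give two eyes and one gives one, with between-eye correlation 0.5 (our assumption). The variance factor is 1 + 0.5 × 24/25 = 1.48. With df 12, t = 3.044 and the half-width is 3.044 × SD × √(1.48/25) = 0.037/0.052/0.074.

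**8. What a 0.2 margin would accept.** With the simultaneous intervals and independent eyes, the upper limit falls below 0.2 with 80% probability when the true mean loss lies 0.037/0.052/0.073 below 0.2 (noncentral t). That is a true loss of 0.163/0.148/0.127.

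**The case against.** ANOVA with adjusted pairwise tests is a conventional way to ask whether a condition has an effect, and the Holm-Sidak step may well include each condition against reference. Condition means are what the ANOVA compares, and a short analysis section that is silent on descriptive statistics does not plan to withhold them. Every estimate proposed here could be computed later from the same data. That P < 0.05 picks up losses far below 0.2 also reflects a sample larger than the stated inputs need. All of this stands, and it limits the weight of the point. It does not remove it. Condition-wise means and SDs would not give the precision of a within-eye change, which depends on the correlation between conditions. An interval chosen after the results are seen is also weaker than one fixed beforehand.

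A reader might infer that the plan will treat non-significance as proof of tolerance. It nowhere says so. A reader might equally infer that a non-significant result always rules out 0.2 logMAR. That holds at the SDs tried with independent eyes, but not at every SD (step 6 of the working).

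The 0.2 itself is open to challenge. It is a large loss to call tolerated, as step 8 shows. The SD in the same sentence carries citation 12, while the reference list as supplied ends at 11, so the basis of these inputs cannot be checked here.

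**Conclusion.** The point holds as a mismatch between a question of size and a plan that only tests. No planned conclusion is wrong; the harm is possible misreading of significant and non-significant results alike. The textual part is certain: no change from reference with an interval is planned, and 0.2 logMAR serves only the sample size. The figures are conditional. They assume 25 independent eyes, a difference SD of 0.05 to 0.10 and, for the adjusted values, a family of 15 pairs. Under those assumptions significance begins at about 0.02 to 0.065 logMAR. The sponsor should make the change because it is cheap and lets the study answer its own question. It is not a fault that invalidates the design.

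The stronger reading, that the trial is set up to declare tolerance wrongly or to hide the size of the loss, is not supported by the documents.

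**What to change.** In the Statistical Analysis section:

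1. Make the main result for each of the five induced conditions the mean within-eye change in logMAR from the reference situation, with a simultaneous 95% confidence interval over the five contrasts.
2. State whether one or both eyes of a patient count. If both, allow for within-patient correlation in the interval.
3. Keep the ANOVA and Holm-Sidak tests as supportive.
4. If the report is to call a condition tolerated, require the upper confidence limit to lie below a margin that the sponsor fixes and justifies before analysis. Do not base the word on non-significance, and do not adopt 0.2 as the margin without support.

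Cost: some wording and one extra table from data already to be collected, with no added eyes or visits. Adjusted intervals are somewhat wider than unadjusted ones (0.028 against 0.021 at SD 0.05), and wider again if both eyes count. Any margin will have to be defended.
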